14.5 Analysis of Safety

Safety is the primary endpoint and described above. Simple descriptive statistics will be used to summarize frequency and grade of AEs (solicited and unsolicited), SAEs, AESIs and MAAEs. Safety Analyses will be performed on Safety Analysis Set.

14.6 Sample Size Justification

The overall mean \log_{10} IgG increase after the third (100 ug) vaccine dose was 0.46 with standard deviation (SD) 0.63. Assuming participants have a 50% lower response to the 50 ug fourth-dose, the expected mean \log_{10} IgG increase is 0.23. Assuming participants have a 100% higher response to the 200 ug fourth-dose, their expected mean \log_{10} IgG increase is 0.91. For 80% power to detect this difference between high-dose and standard-dose groups with a SD of 0.63 for a two-sample t-test with two-sided $\alpha<0.05$ significance, the minimum required sample size is 15 per group. Thus, we will enroll 20 participants in each group. The first 2 participants in the mid and high-dose groups will be enrolled as the sentinel group to ensure an acceptable safety profile before the full group is enrolled.

If the halting criteria is triggered for the high-dose group and further enrollment of this group is not recommended by the study investigators, DSMB or IRB, the study will continue randomized enrollment into the mid-dose and standard-dose groups with a 1:2 ratio to complete the enrollment of 60 participants total. Since the expected immunogenicity difference between the mid-dose and standard-dose group is smaller, we will require more participants to detect a difference between these two groups. The 1:2 enrollment ratio into the mid-dose and standard-dose groups will even the distribution of participants into these two groups. The primary endpoint analysis for safety and reactogenicity will not be affected by a restriction of participants into the mid-dose and standard-dose groups.

14.7 Interim Analysis

Interim analysis of the secondary immunogenicity endpoints (humoral and cellular immunogenicity) may be conducted once all study participants have completed their Day 30 visit and blood draw.

15 DATA COLLECTION, RETENTION AND MONITORING

15.1 Data Collection Instruments

The Investigator will prepare and maintain adequate and accurate source documents designed to record all observations and other pertinent data for each participant treated with the study drug.

Study personnel will enter data from source documents corresponding to each participant into the protocol-specific electronic Case Report Form (eCRF) OR paper CRF when the information corresponding to that visit is available. Participants will not be identified by name in the study database or on any study documents to be collected by the Sponsor (or designee), but will be identified by a participant number.

The Investigator is responsible for all information collected on participants enrolled in this study. All data collected during the course of this study must be reviewed and verified for completeness and accuracy by the Investigator. A copy of the CRF will remain at the Investigator's site at the completion of the study.

15.2 Data Management Procedures

The data will be entered into a secure, de-identified, database. The study coordinators will be responsible for data processing, in accordance with procedural documentation. Database lock will occur once quality assurance procedures have been completed.

All procedures for the handling and analysis of data will be conducted using good computing practices meeting FDA guidelines for the handling and analysis of data for clinical trials.

15.3 Data Quality Control and Reporting

After data have been entered into the study database, a system of computerized data validation checks will be implemented and applied to the database on a regular basis. The study database will be updated in accordance with the resolved queries. All changes to the study database will be documented.

15.4 Archival of Data

The database is safeguarded against unauthorized access by established security procedures; appropriate backup copies of the database and related software files will be maintained. Databases are backed up by the database administrator in conjunction with any updates or changes to the database.

At critical junctures of the protocol (e.g., production of interim reports and final reports), data for analysis is locked and cleaned per established procedures.

15.5 Availability and Retention of Investigational Records

The Sponsor/Investigator must make study data accessible to the monitor, IRB/ and Regulatory Agency (e.g., FDA) inspectors upon request. A file for each participant must be maintained that includes the signed Informed Consent, HIPAA Authorization and Assent Form and copies of all source documentation related to that participant. The Investigator must ensure the reliability and availability of source documents from which the information on the CRF was derived.

All study documents (participant files, signed informed consent forms, copies of CRFs, Study File Notebook, etc.) must be kept secured for a period of two years following marketing of the investigational product or for two years after centers have been notified that the IND has been discontinued. There may be other circumstances for which the Sponsor/Investigator is required to maintain study records.

15.6 Monitoring

This study will be monitored by the UCLA Clinical & Translational Science Institute – Office of Regulatory Affairs (CTSI ORA). Monitoring visits will be conducted according to the U.S. CFR Title 21 Parts 50, 56, and 312 and ICH Guidelines for GCP (E6). By signing this protocol, the Sponsor/Investigator grants permission to the appropriate regulatory authorities to conduct on-site monitoring and/or auditing of all appropriate study documentation.

15.7 Participant Confidentiality

In order to maintain participant confidentiality, only a participant number will identify all study participants on CRFs and other documentation.

ADMINISTRATIVE, ETHICAL, REGULATORY CONSIDERATIONS

The study will be conducted according to the Declaration of Helsinki, Protection of Human Volunteers (21 CFR 50), Institutional Review Boards (21 CFR 56), and Obligations of Clinical Investigators (21 CFR 312).

To maintain confidentiality, all laboratory specimens, evaluation forms, reports and other records will be identified by a coded number and initials only. All study records will be kept in a locked file cabinet and code sheets linking a participant's name to a participant identification number will be stored separately in another locked file cabinet. Clinical information will not be released without written permission of the participant, except as necessary for monitoring by the FDA. The Investigator must also comply with all applicable privacy regulations (e.g., Health Insurance Portability and Accountability Act of 1996, EU Data Protection Directive 95/46/EC).

15.8 Protocol Amendments

Any amendment to the protocol will be written by the Sponsor/Investigator. Protocol amendments cannot be implemented without prior written IRB approval except as necessary to eliminate immediate safety hazards to participants. A protocol amendment intended to eliminate an apparent immediate hazard to participants may be implemented immediately, provided the IRBs are notified within five working days.

15.9 Institutional Review Boards and Independent Ethics Committees

The protocol and consent form will be reviewed and approved by the IRB. Serious adverse experiences regardless of causality will be reported to the IRB in accordance with the standard operating procedures and policies of the IRB, and the Investigator will keep the IRB informed as to the progress of the study. The Investigator will obtain assurance of IRB compliance with regulations.

Any documents that the IRB may need to fulfill its responsibilities (such as protocol, protocol amendments, Investigator's Brochure, consent forms, information concerning participant recruitment, payment or compensation procedures, or other pertinent information) will be submitted to the IRB. The

IRB unconditional approval of the study protocol and the informed consent form will be in the possession of the Investigator before the study is initiated. This approval must refer to the study by exact protocol title and number and should identify the documents reviewed and the date of review.

Protocol and/or informed consent modifications or changes may not be initiated without prior written IRB approval except when necessary to eliminate immediate hazards to the participants or when the change(s) involves only logistical or administrative aspects of the study. Such modifications will be submitted to the IRB and written verification that the modification was submitted and subsequently approved should be obtained.

The IRB must be informed of revisions to other documents originally submitted for review; serious and/or unexpected adverse experiences occurring during the study in accordance with the standard operating procedures and policies of the IRB; new information that may affect adversely the safety of the participants of the conduct of the study; an annual update and/or request for re-approval; and when the study has been completed.

15.10 Informed Consent Form

Informed consent will be obtained in accordance with the Declaration of Helsinki, ICH GCP, US Code of Federal Regulations for Protection of Human Subjects (21 CFR 50.25[a,b], CFR 50.27, and CFR Part 56, Subpart A), the Health Insurance Portability and Accountability Act (HIPAA, if applicable), and local regulations.

The Investigator will prepare the informed consent form, and HIPAA authorization and provide the documents to the IRB/. The consent form generated by the Investigator must be approved by the IRB. The written consent document will embody the elements of informed consent as described in the International Conference on Harmonisation and will also comply with local regulations. The Investigator will include the IRB/ -approved copy of the Informed Consent Form in the study file.

A properly executed, written, informed consent will be obtained from each participant prior to entering the participant into the trial. Information should be given in both oral and written form and participants (or their legal representatives) must be given ample opportunity to inquire about details of the study. If a participant is unable to sign the informed consent form (ICF) and the HIPAA authorization, a legal representative may sign for the participant. A copy of the signed consent form) will be given to the participant or legal representative of the participant and the original will be maintained with the participant's records.

15.11 Publications

The publication or presentation of any study results shall comply with all applicable privacy laws, including, but not limited to, the Health Insurance Portability and Accountability Act of 1996.

15.12 Investigator Responsibilities

By signing the Agreement of Investigator form, the Investigator agrees to:

1. Conduct the study in accordance with the protocol and only make changes after notifying the Sponsor (or designee), except when to protect the safety, rights or welfare of participants.
2. Personally, conduct or supervise the study (or investigation).

Phase I/II, Open-label Dose-finding Trial of High-Dose mRNA-1273 Booster for Lung Transplant Recipients
Confidential

3. Ensure that the requirements relating to obtaining informed consent and IRB review and approval meet federal guidelines, as stated in § 21 CFR, parts 50 and 56.
4. Report to the Sponsor or designee any AEs that occur in the course of the study, in accordance with §21 CFR 312.64.
5. Ensure that all associates, colleagues and employees assisting in the conduct of the study are informed about their obligations in meeting the above commitments.
6. Maintain adequate and accurate records in accordance with §21 CFR 312.62 and to make those records available for inspection with the Sponsor (or designee).
7. Ensure that an IRB that complies with the requirements of §21 CFR part 56 will be responsible for initial and continuing review and approval of the clinical study.
8. Promptly report to the IRB and the Sponsor (or designee) all changes in the research activity and all unanticipated problems involving risks to participants or others (to include amendments and IND safety reports).
9. Seek IRB approval before any changes are made in the research study, except when necessary to eliminate hazards to the participants.
10. Comply with all other requirements regarding the obligations of clinical investigators and all other pertinent requirements listed in § 21 CFR part 312.

APPENDIX 1. SCHEDULE OF EVENTS

	Screening Day -30 to Day 0	Visit 1 Day 1 Clinic	Visit 2 Day 3 Phone +/-1 day	Visit 3 Day 7 Clinic +/-2 days	Visit 4 Day 30 Clinic +/-7 days	Visit 5 Day 90 Phone +/-7 days	Visit 6 Day 180 Phone +/-7 days	Unscheduled visit as needed
Informed Consent		X						
Demographic data		X						
Medical History		X						
Eligibility review	X	X						
Con meds		X						
Pre-study meds		X						
Review CoV vaccinations		X						
Height		X						
Weight		X		X	X			
Vital Signs (HR, BP, temperature, oximetry)		X		X	X			
Full physical exam		X						X

Phase I/II, Open-label Dose-finding Trial of High-Dose mRNA-1273 Booster for Lung Transplant Recipients
Confidential

Targeted physical exam				X	X			
Blood draw*		X		X	X			X
Group assignment		X						
IP administration		X						
30-minute post-dose observation		X						
Review AEs, SAEs, AESIs, MAAEs			X	X	X	X	X	X
Review myocarditis and pericarditis symptoms			X	X	X	X	X	X
Dispense daily diary		X						
Diary review			X	X				
Pregnancy test (women of child-bearing potential)		X						
Birth control history (women of child-bearing potential)		X						
Review participants' use of appropriate birth control (if applicable)		X						

*Baseline labs must be drawn before vaccine dose. Day 7 must be drawn +/- 2 days. All other labs can be drawn +/- 7 days.

APPENDIX 2: ADVERSE EVENTS OF SPECIAL INTEREST (AESI) TERMS

The Investigator's medical judgement must be applied to assess an event as an AESI, as most AESIs are based on medical concepts. The table below does not provide a comprehensive list of terms.

The following table describes events/medical concepts that are of interest in COVID-19 vaccine safety surveillance. Some are specific to vaccines; however, some are of interest due to their occurrence in the context of concurrent or recent COVID-19. Events falling into the descriptions below should be reported as AESIs, per protocol, even when they occur during/following COVID infection.

Please note: COVID-19 itself is not an AESI.

Medical Concept	Medical Concept Descriptions/Guidance
0. Not an AESI	
1. Anosmia, Ageusia	
• New onset of anosmia or ageusia associated with COVID-19 or idiopathic etiology• DOES NOT INCLUDE anosmia or ageusia associated with sinus/nasal congestion, congenital, or traumatic etiologies
2. Subacute thyroiditis	
• Acute inflammatory disease of the thyroid (immune-mediated or idiopathic)• DOES NOT INCLUDE new onset of chronic thyroiditis
3. Acute pancreatitis	
• New onset of pancreatitis in the absence of a clear, alternate etiology, such as alcohol, gallstones, trauma, recent invasive procedure, etc.
4. Appendicitis	
• Any event of appendicitis
5. Rhabdomyolysis	
• New onset of rhabdomyolysis in the absence of a clear, alternate etiology, such as drug/alcohol abuse, excessive exercise, trauma, etc.
6. Acute respiratory distress syndrome (ARDS)	
• New onset of ARDS/respiratory failure due to acute inflammatory lung injury• DOES NOT INCLUDE non-specific symptoms of shortness of breath or dyspnea, nor events with underlying etiologies of heart failure or fluid overload
7. Coagulation disorders	
• New onset of thrombosis, thromboembolic event, or non-traumatic hemorrhage/bleeding disorder (ex. stroke, DVT, pulmonary embolism, disseminated intravascular coagulation (DIC), etc.)
8. Acute cardiovascular injury	
• New onset of clinically confirmed, acute cardiovascular injury, such as myocarditis, pericarditis, arrhythmia confirmed by ECG (ex. atrial fibrillation, atrial flutter, supraventricular tachycardia), stress cardiomyopathy, heart failure, acute coronary syndrome, myocardial infarction, etc.• DOES NOT INCLUDE transient sinus tachycardia/bradycardia, non-specific symptoms such as palpitations, racing heart, heart fluttering or pounding, irregular heartbeats, shortness of breath, chest pain/discomfort, etc.

Medical Concept	Medical Concept Descriptions/Guidance
9. Acute kidney injury	
 • New onset of acute kidney injury or acute renal failure in the absence of a clear, alternate etiology, such as urinary tract infection/urosepsis, trauma, tumor, nephrotoxic medications/substances, etc.; • Increase in serum creatinine by ≥ 0.3 mg/dl (or ≥ 26.5 μmol/l) within 48 hours; OR • Increase in serum creatinine to ≥ 1.5 times baseline, known or presumed to have occurred within prior 7 days
10. Acute liver injury	
 • New onset in the absence of a clear, alternate etiology, such as trauma, tumor, hepatotoxic medications/substances, etc.: • >3-fold elevation above the upper normal limit for ALT or AST; OR • >2-fold elevation above the upper normal limit for total serum bilirubin or GGT or ALP
11. Dermatologic findings	
 • Chilblain-like lesions • Single organ cutaneous vasculitis • Erythema multiforme • Bullous rash • Severe cutaneous adverse reactions, such as Stevens-Johnson syndrome, Toxic epidermal necrolysis, Drug reaction with eosinophilia and systemic symptoms (DRESS), fixed drug eruptions, and necrotic or exfoliative reactions
12 Systemic inflammatory syndromes	
 • Multisystem inflammatory syndrome in adults (MIS-A) or children (MIS-C) • Kawasaki's disease • Hemophagocytic lymphohistiocytosis (HLH)
13. Thrombocytopenia	
 • Platelet count $< 150 \times 10^9/L$ (thrombocytopenia) • New clinical diagnosis, or worsening, of thrombocytopenic condition, such as immune thrombocytopenia, thrombocytopenic purpura, or HELLP syndrome
14. Acute aseptic arthritis	
Clinical syndrome characterized by acute onset of signs and symptoms of joint inflammation without recent trauma for a period of no longer than 6 weeks, synovial increased leukocyte count and the absence of microorganisms on Gram stain, routine culture and/or PCR.
 
 • DOES NOT INCLUDE new onset of chronic arthritic conditions
15. New onset, or worsening, of neurological disease	
 • Immune-mediated neurological disorders • Guillain-Barre Syndrome • Acute disseminated encephalomyelitis (ADEM) • Peripheral facial nerve palsy (Bell's palsy) • Transverse myelitis • Encephalitis/Encephalomyelitis • Aseptic meningitis • Seizures/convulsions/epilepsy • Narcolepsy/hypersomnia
16. Anaphylaxis	
 • Anaphylaxis associated with study drug administration

Medical Concept	Medical Concept Descriptions/Guidance
17. Other syndromes	
• Fibromyalgia• Postural Orthostatic Tachycardia Syndrome• Chronic Fatigue Syndrome• Myalgic encephalomyelitis• Post viral fatigue syndrome• Myasthenia gravis

APPENDIX 3: TABLE OF LABORATORY ABNORMALITIES

Test	Mild (Grade 1)	Moderate (Grade 2)	Severe (Grade 3)	Potentially Life Threatening (Grade 4)
Sodium (Hyponatremia) mEq/L	132 - 134	130 - 131	125 - 129	< 125
Sodium (Hypernatremia) mEq/L	144 - 145	146 - 147	148 - 150	> 150
Potassium (Hyperkalemia) mEq/L	5.4 - 5.6	5.6 - 5.8	5.8 - 6.0	> 6.0
Potassium (Hypokalemia) mEq/L	3.2 - 3.5	3.0 - 3.1	2.8 - 2.9	< 2.8
Glucose (Hypoglycemia) mg/dL	65 - 69	55 - 64	45 - 54	< 45
Glucose (Hyperglycemia) mg/dL				
Fasting	110 - 110	111 - 125	> 125	Requires insulin
Random	110 - 125	126 - 200	> 200	Requires insulin
Blood Urea Nitrogen (BUN) mg/dL	30 - 35	35 - 40	> 40	Requires dialysis
				> 3.2 or Requires dialysis
Creatinine (Cr) mg/dL	1.8 - 2.3	2.4 - 2.8	2.9 - 3.2	
Calcium (Hypocalcemia) mg/dL	8.0 - 8.4	7.5 - 7.9	7.0 - 7.4	< 7.0
Calcium (Hypercalcemia) mg/dL	10.5 - 11.0	11.1 - 11.5	11.6 - 12.0	> 12.0
Magnesium (Hypomagnesemia) mg/dL	1.3 - 1.5	1.0 - 1.2	0.7 - 0.9	< 0.7
Phosphorus (Hypophosphatemia) mg/dL	2.3 - 2.5	2.0 - 2.2	1.6 - 1.9	< 1.6
CPK	1.25 - 1.5 x ULN	1.6 - 3.0 x ULN	3.1 - 10 x ULN	> 10 x ULN
Albumin (Hypoalbuminemia) mg/dL	2.5 - 2.8	2.1 - 2.4	< 2.1	---
Protein (Hipoproteinemia) mg/dL	5.0 - 5.5	4.4 - 4.9	< 4.4	---
Alkaline Phosphatase - Increase by Factor	1.1 - 2.0 x ULN	1.6 - 3.0 x ULN	3.1 - 10 x ULN	> 10 x ULN
Liver function Tests (ALT, AST) - Increase by Factor	1.1 - 2.5 x ULN	2.6 - 5.0 ULN	5.1 - 10 x ULN	> 10 x ULN
Bilirubin - when accompanied by any increase in LFTs - Increase by Factor	1.1 - 1.25 x ULN	1.26 - 1.5 x ULN	1.51 - 1.75 x ULN	> 1.75 x ULN
Bilirubin - when LFTs are normal - Increase by Factor	1.1 - 1.5 x ULN	1.6 - 2.0 x ULN	2.0 - 3.0 x ULN	> 3.0 x ULN
Pancreatic enzymes (Amylase, lipase)	1.1 - 1.5 x ULN	1.6 - 2.0 x ULN	2.0 - 5.0 x ULN	> 5.0 x ULN
Hemoglobin (Female)	8.6 - 9.1	8.1 - 8.5	7.0 - 8.0	< 7.0
Hemoglobin (Female) change from baseline value gm/dL	1.2 - 1.5	1.6 - 2.0	2.1 - 5.0	> 5.0
Hemoglobin (Male)	9.1 - 9.5	8.6 - 9.0	7.5 - 8.5	< 7.5
Hemoglobin (Male) change from baseline value gm/dL	1.2 - 1.5	1.6 - 2.0	2.1 - 5.0	> 5.0
WBC (High) cell/mm ³	15,000 - 20,000	20,001 - 25,000	25,001 - 30,000	> 30,000
WBC (Low) cell/mm ³	1,501 - 2,000	1,001 - 1,500	500 - 1,000	< 500
Lymphocyte (Low) cell/mm ³	601 - 800	401 - 600	200 - 400	< 200
Neutrophil (Low) cell/mm ³	701 - 1,000	501 - 700	401 - 500	< 400
Eosinophils (High) cell/mm ³	650 - 1,500	1,501 - 5,000	> 5,000	Hypereosinophilic
Platelets (Low) cell/mm ³	60,001 - 80,000	40,001 - 60,000	> 25,000 - 40,000	< 25,000
Prothrombin time (PT) - Increase by Factor	1.11 - 1.2	1.21 - 1.3	1.31 - 1.4 x ULN	> 1.4 ULN
Partial thrombinoplastin time (PTT) - Increase by Factor	1.31 - 1.4	1.41 - 1.5	1.51 - 1.6 x ULN	> 1.6 ULN
Fibrinogen (High) mg/dL	400 - 500	501 - 600	> 600	---
				< 100 or associated with gross bleeding or disseminated intravascular coagulation
Fibrinogen (Low) mg/dL	150 - 200	125 - 149	100 - 124	

[1] ULN - Upper limit of normal.

[2] Values highlighted in yellow are adjusted from "Guidance for Industry Toxicity Grading Scale for Healthy Adult and Adolescent Volunteers Enrolled in Preventive Vaccine Clinical Trials" to reflect immunosuppressed lung transplant population.

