11 ADVERSE EXPERIENCE REPORTING AND DOCUMENTATION

11.1 Adverse Events

An adverse event (AE) is any untoward medical occurrence in a clinical investigation of a participant administered a pharmaceutical product and that does not necessarily have a causal relationship with the treatment. An AE is therefore any unfavorable and unintended sign (including an abnormal laboratory

finding), symptom or disease temporally associated with the administration of an investigational product, whether or not related to that investigational product. Any medical condition that is present at the time that the subject is screened will be considered as baseline and not reported as an AE. However, if the severity of any pre-existing medical condition increases, it will be recorded as an AE.

AEs can be further divided into solicited AEs and unsolicited AEs. Solicited AEs are those for which the study team will specifically query the subject whether they occurred. Unsolicited AEs are those events that the subject report occurring without being queried about the specific event.

A suspected adverse event is one for which there is a ‘reasonable possibility’ that the drug caused the adverse event. A ‘reasonable possibility’ means there is evidence to suggest a causal relationship between the drug and the adverse event, but implies a lesser degree of certainty about causality compared with an adverse event. An unexpected AE is one of a type not identified in nature, severity, or frequency in the current Investigator’s Brochure or of greater severity or frequency than expected based on the information in the Investigator’s Brochure. All AEs will be assessed for severity and relationship to study intervention (Tables 3 and 4). Suspected, Unexpected, Serious Adverse Reactions (SUSAR) is an adverse event where a causal relationship with the study drug is at least possible but not listed in the Investigator Brochure (IB), Package Insert, and/or Summary of Product Characteristics and includes any of the following: suspected AE, unexpected AE and serious adverse experience (SAE). Episodes of myocarditis or pericarditis occurring in temporal association with vaccination will be reported as a SUSAR. Medically attended adverse event (MAAE) is defined as hospitalization, an emergency room visit or an otherwise unscheduled visit to or from medical personnel for any reason.

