If you experience any grade 4 symptom from your daily diary, or any other severe symptoms that prevents your daily activity AND requires you to see a doctor, please call [name] immediately at [contact]. The operator will answer the call, please tell them that you would like to "page [name]". [name] or another covering Dr will call you back.					

Source: Guidance for industry – Toxicity Grading Scale for Healthy Adult and Adolescent Volunteers Enrolled in Preventive Vaccine Clinical Trials; tables for clinical abnormalities ([DHHS 2007](#)).

Unsolicited Adverse Events

All AEs spontaneously reported by the subject and/or in response to an open question from study staff or revealed by observation, physical examination or other diagnostic procedures must be recorded on the appropriate CRF. Unsolicited AEs of all severities will be reported from the time of study product administration through Day 30. After Day 30, only SAEs and AESIs will be reported through the end of the study (Day 180).

AE Severity

”Table 3: Solicited Adverse Reactions and Grading” will be used to assess and grade solicited AE severity. ”Appendix 3: Table of Laboratory Abnormalities” will be used to grade any laboratory abnormalities observed. If the adverse event is not covered in Table 3 and Appendix 3, the guidelines shown in Table 4 below should be used to grade severity. It should be pointed out that the term “severe” is a measure of intensity and that a severe AE is not necessarily serious.

Table 4. AE Severity Grading

Severity (Toxicity Grade)	Description
Mild (1)	These events do not interfere with the participant’s daily activities.
Moderate (2)	These events cause some interference with the participant’s daily activities and require limited or no medical intervention.
Severe (3)	These events prevent the participant’s daily activity and require intensive therapeutic intervention.

AE Relationship to Study Drug

The relationship of an AE to the study drug should be assessed using the following guidelines in Table 5.

Table 5. AE Relationship to Study Drug

Relationship to Drug	Comment
----------------------	---------

Definitely	Previously known toxicity of agent; or an event that follows a reasonable temporal sequence from administration of the drug; that follows a known or expected response pattern to the suspected drug; that is confirmed by stopping or reducing the dosage of the drug; and that is not explained by any other reasonable hypothesis.

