14.3 Analysis of Primary Endpoint

Safety will be measured by the frequency and grade of AEs (solicited and unsolicited), SAEs, AESIs, MAAEs. Reactogenicity will be measured by the occurrence and severity of solicited injection site and systemic reactions. Simple descriptive statistics will be used to summarize toxicities in terms of type, severity and minimum or maximum values for laboratory measures, time of onset, duration, and reversibility or outcome. Tables will be created to summarize these toxicities and side effects. Safety Analyses will be performed on Safety Analysis Set.

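### Five rows of Appendix 3 give one laboratory value two severity grades and two rows leave a value ungraded, so the grade of some laboratory adverse events is undefined

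*Combined protocol and SAP*

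**What the plan says.** Section 11.1 counts as an adverse event "any unfavorable and unintended sign (including an abnormal laboratory" finding. Under AE Severity it sends solicited reactions to Table 3 and says that Appendix 3 "will be used to grade any laboratory abnormalities observed". Table 4 is only the fallback for severity: "If the adverse event is not covered in Table 3 and Appendix 3, the guidelines shown in Table 4 below should be used to grade".

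Section 5.1 makes the frequency and grade of unsolicited adverse events to Day 30 part of the primary safety endpoint. Section 14.3 will "summarize toxicities in terms of type, severity and minimum or maximum values for laboratory measures".

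In Appendix 3, the first two alkaline phosphatase bands are "1.1 - 2.0 x ULN 1.6 - 3.0 x ULN". The first three bands for high potassium are "5.4 - 5.6 5.6 - 5.8 5.8 - 6.0". Grades 2 and 3 are "1.6 - 2.0 x ULN 2.0 - 3.0 x ULN" for bilirubin with normal liver tests and "1.6 - 2.0 x ULN 2.0 - 5.0 x ULN" for pancreatic enzymes. BUN has 30 to 35 as Grade 1 and 35 to 40 as Grade 2. Footnote [2] says that some values, highlighted in the table, were changed from the source scale to suit an immunosuppressed lung transplant population.

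**The concern.** A grading scale should give each value one grade. In five rows of Appendix 3 a value belongs to two grades, and in two rows a value belongs to none. Two people applying the table correctly could then record different severities for the same result.

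At three of the shared values the choice is between moderate and severe. Dose is open-label and is disclosed at Visit 1 (Section 10.2), and the mid-dose group is filled before the high-dose group opens (Section 4.1). An undefined grade would therefore be settled case by case, by staff who can know the dose, and at different times for the two higher-dose groups.

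**Working it through.** The plan states no figure to reproduce. The check compares the bands with one another and then traces where the grades are used.

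**1. Overlap test.** For an analyte whose severity rises with the value, let adjacent grades be closed bands a to b and c to d. They overlap if c ≤ b, and the overlap has width b − c. All 35 graded rows were tested at the precision printed in the table, with the test mirrored for analytes that worsen as they fall.

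| Row | Grades | b | c | Width | Values with two grades |
|---|---|---|---|---|---|
| Alkaline phosphatase, x ULN | 1 and 2 | 2.0 | 1.6 | 0.4 | 1.6, 1.7, 1.8, 1.9, 2.0 |
| Potassium high, mEq/L | 1 and 2 | 5.6 | 5.6 | 0 | 5.6 |
| Potassium high, mEq/L | 2 and 3 | 5.8 | 5.8 | 0 | 5.8 |
| BUN, mg/dL | 1 and 2 | 35 | 35 | 0 | 35 |
| Bilirubin, normal liver tests, x ULN | 2 and 3 | 2.0 | 2.0 | 0 | 2.0 |
| Pancreatic enzymes, x ULN | 2 and 3 | 2.0 | 2.0 | 0 | 2.0 |

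Five of 35 rows overlap. They contain 5 + 2 + 1 + 1 + 1 = 10 doubly graded values at printed precision: seven between Grades 1 and 2, and three between Grades 2 and 3. None involves Grade 4. Only alkaline phosphatase overlaps over a range.

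**2. Gap test.** Neutrophil Grade 3 is 401 to 500 and Grade 4 is below 400, so 400 has no grade. Platelet Grade 3 is above 25,000 (to 40,000) and Grade 4 is below 25,000, so 25,000 has no grade.

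**3. Is sharing a boundary a convention of the table?** No. Other rows separate their bands: high calcium goes from 11.0 to 11.1, and ALT/AST from 2.5 to 2.6 x ULN.

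**4. Is there a tie rule?** None is stated. Table 4 applies only to events that Table 3 and Appendix 3 do not cover, and a value in two bands is covered. Table 4 might be read as reaching the two ungraded values, but it grades by effect on daily activity and level of intervention, not by laboratory value.

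**5. Where do these grades go?** They reach the severity summary of unsolicited adverse events to Day 30, for events that are laboratory findings. Other outputs do not use them:
- Solicited reactions are graded from Table 3 (Section 11.1).
- The grade-based halting rules cite Table 3 (Sections 12.2 and 12.3).
- SAEs, AESIs and MAAEs are collected by frequency (Section 5.1). The laboratory-based AESIs in Appendix 2 have their own cut-offs.
- Laboratory minima and maxima need no grade.

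**6. How often could it arise?** Scheduled draws are research assays plus stored troponin, CK and cytokines (Section 9.2.1), and the CPK row has no overlap. A metabolic panel and blood count may be checked at unscheduled visits (Sections 9.2.2 and 10.8). Amylase and lipase are on no listed panel.

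**The case against.** The strongest reply is that this hardly matters. None of the affected analytes is on a scheduled draw. Four of the five overlapping rows conflict only at exact boundary values, and the one true range separates mild from moderate. The trial has a single site, and the safety analysis is descriptive, so no test turns on a grade. The planned minima, maxima and participant listings (Section 14.1) would show the raw values. All of this stands, and it limits the point to a small one. It does not give a grade to an alkaline phosphatase of 1.8 x ULN. Because Section 11.1 reaches any abnormality observed, results from routine care could also need grading.

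A reader might infer more than the documents support:
- That the primary severity tables as a whole depend on the grader. They do not: only laboratory adverse events in these rows are exposed.
- That a pause could be triggered or missed. The grade-based halting rules do not use Appendix 3.
- That the overlap share measures impact. For alkaline phosphatase, 0.4 of a Grade 1 band 0.9 wide (2.0 − 1.1) is 44%, but this is a share of band width, not of participants. Likewise, one event in a group of 20 is always 5 percentage points (1/20), whatever its cause.
- That the higher grade is the safe default. It would in effect end alkaline phosphatase Grade 1 at 1.5 x ULN. If 2.0 was one of the deliberate adjustments in footnote [2], the default would silently cancel it.

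**Conclusion.** The point holds as a table inconsistency with a narrow effect. At ten printed values in five rows the grade is double, and at two further values it is missing. Section 11.1 makes this table the operative scale and gives no tie rule. Part of the primary summary, the severity of laboratory adverse events in these rows, is therefore undefined at those values in an open-label trial.

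The number of participants affected cannot be estimated, because the documents give no expected count of unscheduled or routine-care results. It is likely to be small. Two assumptions matter. First, that the metabolic panel includes potassium, BUN, alkaline phosphatase and bilirubin, and that the blood count includes platelets; the documents do not list their contents. Second, that results are recorded at the precision printed in the table. The highlighting that marks adjusted values is not visible in the text reviewed, so it cannot be said whether the overlaps came from those adjustments, or which limits were intended.

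**What to change.** Before any data are graded, the sponsor should check the seven rows (five overlaps, two gaps) against the source scale and its own intended adjustments, and reissue them so that the bands neither overlap nor leave gaps. The sponsor must choose the cut-offs; a default such as always taking the higher grade should not stand in for that choice.

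Laboratory grades should then be derived by program from the recorded value and the laboratory's ULN. For rows expressed as multiples of ULN, either write the bands as contiguous intervals or state a rounding rule: a computed ratio can fall between printed limits, as 2.55 x ULN does for ALT/AST.

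The cost is a minor table correction and a little programming. No visit, sample or sample-size assumption changes.
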